7.2 Description of Activities

- *Telephone data collection surveys* – participants will complete the validated measures tested as outcomes or mediators listed above as well as other measures to help characterize health and functional status, quality of life, and satisfaction with the intervention, at baseline and/or 8 weeks from baseline. Participants will be sent response options for each of the survey scales prior to their scheduled telephone survey appointment so they can see the response options and follow along. If participants do not have the survey scales, they can either reschedule or continue with the survey if they prefer (staff will read responses for each question/item on the survey).
- *Randomization* – occurs after a participant completes their baseline telephone survey.
- *STEP-UP Program (Intervention)* – See Table in Section 6.2 for details of intervention activities and flow..

8 SAFETY

8.1 Potential Risks & Benefits - See Section 1.4

8.2 Event Reporting Schedule

This study will use a study-specific reporting schedule for adverse events, protocol deviations, ORIOs and unanticipated problems. The reporting schedule can be found in eResearch, Section 32.

8.3 Definitions for Events

We will use standard definitions of AEs/SAEs as follows:

Adverse Event (AE): Any untoward or unfavorable medical occurrence in a human study participant, including any abnormal sign (e.g., abnormal physical exam or laboratory finding), symptom, or disease, temporally associated with the participants' involvement in the research, whether or not considered related to participation in the research. The most likely example for the present pilot study is elevated psychological distress.

Serious Adverse Event (SAE): Any adverse event that: Results in death; Is life threatening or places the participant at immediate risk of death from the event as it occurred; Requires or prolongs

hospitalization; Causes persistent or significant disability or incapacity; Results in congenital anomalies or birth defects; Is another condition which investigators judge to represent significant hazards. An example in the present study is a hospitalization.

Unanticipated Problem (UP):

Defined by DHHS 45 CFR part 46 as any incident, experience, or outcome that **meets all the following criteria:**

- unexpected, in terms of nature, severity, or frequency, given (a) the research procedures that are described in the protocol-related documents, such as the IRB-approved research protocol and informed consent document; and (b) the characteristics of the study population;
- related or possibly related to participation in the research (in this guidance document, possibly related means there is a reasonable possibility that the incident, experience, or outcome may have been caused by the procedures involved in the research);
- suggests that the research places participants or others at a greater risk of harm (including physical, psychological, economic, or social harm) than was previously known or recognized.

8.4 Classification of Adverse Events

8.4.1 Severity of Event

We will use the standard grading scale in use by the University of Michigan Institutional Review Board - Health Sciences and Behavioral Sciences (UM IRB-HSBS) as follows:

Grading scale:

1. No adverse event
2. Mild AE – No treatment needed
3. Moderate AE – Resolved with treatment
4. Severe AE – Inability to carry on normal activities, required professional medical attention
5. Life-threatening or disabling AE
6. Fatal AE

8.4.2 Relationship to Participation

We will use the standard relatedness scale in use by the University of Michigan Institutional Review Board - Health Sciences and Behavioral Sciences (UM IRB-HSBS) as follows:

Relatedness scale:

- Definitely related
- Probably related
- Possibly related
- Unlikely to be related
- Definitely not related

Expectedness

- Unexpected
- Expected

8.4.3 Expectedness

For an event to be classified as “expected” it should have been addressed in at least one of the following sources: this document, the research application, literature, proposal document, informed consent, or associated with the characteristics of the study population.

7.4.4. Process for identifying AEs and SAEs

Given the low likelihood of adverse events in this study, and the short length of the active study period (8 weeks for an individual participant), passive monitoring for adverse events will be done by the PI, other research staff, and community health workers on an ongoing basis and will be reported to the IRB and other entities as described in the “AE/SAE Reporting” section below.

It is possible that we will learn of adverse health-related events when conducting follow-up interviews; it is also possible that community health workers will learn of such events when speaking with participants or attempting to make contact. It is also possible that the study coordinator/research assistants providing technical or other support to participants will learn of such events. These staff will all be trained to recognize and immediately report anything that could potentially be an adverse event.

AE/SAE Reporting:

All AEs and SAEs will be collected on an Adverse Event form in the study’s REDCap database and will be reported immediately to the PI by the person learning of the event (generally, study staff, or community health workers).

The PI or designated staff member will complete the UM IRB-HSBS Adverse Event Reporting form. Next steps will include the following:

- For all expedited AE/SAE/UP reports, the Cornell Roybal Directors, and/or NIA PO may determine if full DSMB review is required.
- All **adverse events that are both serious (SAE) and unexpected** (have not been defined as expected in the DSMP), should be reported to IRB, NIA PO and to Cornell Roybal Directors [name] and [name].
- The summary of all other SAEs (i.e., expected or not related SAEs) will be reported to NIA Program Officer and to the Cornell Roybal Directors **quarterly**, or as requested by the Cornell Roybal Directors.
- All **unexpected** deaths will be reported within 24 hours to the NIA PO, Cornell Roybal Directors, and IRB.
- Unanticipated Problems (UP) will be reported to IRB, NIA PO and to the Cornell Roybal Directors **within 48 hours** of the study's knowledge of UP. The Unanticipated Problems report must include a corrective plan and measures to prevent reoccurrence. Reports of Unanticipated Problems, as defined above, should be forwarded to OHRP using [contact], typically within two weeks of the event.
- AEs will be reported per IRB policies. They should also be reported to the NIA Program Officer and to the Roybal Directors at minimum annually, or at a frequency requested by NIA and/or by the Cornell Roybal.

No related AEs or SAEs are expected for this minimal-risk study of a behavioral intervention (i.e., events known to be associated with the intervention or condition under study, i.e., a cognitive-behavioral

intervention for chronic musculoskeletal pain). Although participants will be encouraged to become more physically active, this will take the form of incremental increases in existing low to moderate intensity physical activities (e.g., walking) and trying the exercises in the NIA *Workout To Go* booklet that has been selected specifically to be done safely by older adults.

However, we do expect unrelated AEs and SAEs, based on the high morbidity and multimorbidity of this population (i.e., adults who are 50+ years of age, most or all of whom will be from underserved and/or marginalized populations). These **unrelated but expected** AEs and SAEs could include hospitalizations, deaths, and/or other moderate to severe illness-related events during the study period that are related to age and pre-existing health conditions and unrelated to study participation. Nonetheless, if these occur, they will be reported as AEs or SAEs and the appropriate steps as outlined above will be taken.

Below are the specific events that will trigger reporting to the parties described above:

Acute Alerts/Serious Adverse Events

- Hospitalization of Study Participant
- Institutionalization of Participant
- Emergency Room Visit of Participant
- Death of Participant

Safety Alerts/Adverse Events

- Severe Medical Problem of Participant
- Participant threatens to harm him or herself or others

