All participant study information will be kept in a secure, HIPAA-compliant REDCap database within the University of Michigan. Additional study files will be secured in a HIPAA-compliant University of Michigan team Dropbox account.

Throughout the study, IRB guidelines and best practices in human subjects research will be followed to ensure the privacy and integrity of the information we collect. Any breach of confidentiality will be immediately reported to the PI and to the University of Michigan Health Sciences and Behavioral Sciences IRB. In addition, any complaints or concerns expressed to the study staff by participants, providers, or anyone else affected by this study will be immediately reported to the PI, and as appropriate, to the IRB.

All study staff, including community health workers, and research assistants will complete the online Social and Behavioral Research Best Practices course (<https://research-compliance.umich.edu/hrpp-education-resources>) which fulfills the NIH Good Clinical Practice requirement and the web-based University of Michigan's Responsible Conduct of Research Training Program, known as PEERRS (Program for Education and Evaluation in Responsible Research and Scholarship). Proof of their certification and completion of the training program will be kept on file. Training of staff will include information about the importance of privacy and confidentiality and specific techniques to maintain confidentiality of all information in the context of this study. Regular study team meetings will be used to ensure that all data quality and IRB policies and procedures are being followed.

All research data presented in reports, presentations, or manuscripts will be in aggregate and/or de-identified form only.

3. Physical Injury (FREQUENCY: infrequent, SERIOUSNESS: Mild)

Another possible risk is minor physical injury from doing physical activity that is encouraged by the STEP-UP program. Participants are encouraged to engage in physical activity of their choice, at a level that is comfortable for them. As with any physical activity, it is possible that participants could experience an injury while doing physical activity, like muscle strain. To minimize this risk, the STEP-UP Community Health Worker will guide participants in increasing activity levels slowly and will encourage them to check with their doctor if they do not know whether a specific activity is appropriate.

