Participants will also engage in a values-clarification exercise (“What Matters Most”, in the domains of Connecting, Enjoying Life, Managing Health, Functioning) and goal-setting process, adapted from the Patient Priorities Care model. Participants will set meaningful activity goals that reflect their values. This process will include completing a “My Pain Priorities” summary sheet that can be shared with their provider, which includes information about care that they perceive as helpful or burdensome. The CHW will also complete a fillable form for each participant that states that they are taking part in the STEP-UP study and will include the information from the My Pain Priorities summary sheet. The CHW or study staff will fax this form to the WWFHC secure fax line for patient information and it will be uploaded by WWFHC into the patient’s Electronic Health Record (EHR). This is a way for the CHW to put information into the EHR without having to have their own access to the EHR system. By adding the participant’s My Pain Priorities summary sheet to their EHR, the participant’s healthcare providers can see what the participant’s goals and values are for a patient-centered approach to pain management. This may better facilitate conversations between the patient and the provider related to values and priorities. At this orientation, participants will also learn how to access the audio recordings (podcasts) and they will choose a time for weekly telephone sessions with the CHW.

Subsequent sessions: Participants will be asked to listen to one podcast episode per week, each presenting a new self-management skill along with motivational elements to try out the new skill. Podcast audiofiles will be made available on a website or “dial in.” Each week, participants will receive a reminder text, voicemail, or phone call from the CHW (based on their preferences) encouraging them to listen to that week’s podcast episode, complete tasks as described in the workbook, and continue to work on their values-informed behavioral goal.

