6.10 Withdrawal from the Study

If participants withdraw or decline to finish the intervention, every effort should be made to gather primary outcome data (pain interference) as well as a query about adverse events.

- The goal is to collect the information as close to the designated follow-up assessment as possible (8 weeks). Participants need to complete the assessment within one month of the follow-up date in order to be counted as non-missing.
- For intervention group participants wishing to discontinue participation in the intervention, the study team member will ask to call them during the scheduled follow-up window.
- Participants who state that they wish to withdraw completely from the study will not be contacted further.

The reason for participant discontinuation or withdrawal from the study will be recorded in REDCap. Participants who sign the informed consent form and are randomized to the intervention but do not begin it will not be replaced, due to the short overall study period. Participants who sign the informed consent form, and are randomized and receive the study intervention, and subsequently withdraw, or are discontinued from the study, will not be replaced.

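### Adverse events are captured passively while scheduled contact before week 8 differs by arm, so reportable events can be missed, more easily in controls

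*Combined protocol and SAP*

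**What the plan says.** Section 7.4.4 (printed with that number inside Section 8, Safety) sets the method: "passive monitoring for adverse events will be done by the PI, other research staff, and community health workers". It names three routes, each described as a possibility:

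- the survey call: "It is possible that we will learn of adverse health-related events when conducting follow-up interviews";
- the CHW: "it is also possible that community health workers will learn of such events when speaking with participants or attempting to make contact";
- support staff: the "study coordinator/research assistants providing technical or other support to participants will learn of such events".

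Staff are to be trained to recognize and report events at once. The same section expects unrelated adverse and serious adverse events because the population is older and multimorbid. It lists hospitalization, institutionalization, emergency room visits and death among the reporting triggers, without limiting them to one arm.

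On contact, Section 6.2 gives intervention participants six weekly CHW sessions and a weekly CHW reminder by text, voicemail or call. Section 7.1 marks CHW sessions as intervention group only. Section 6.3 gives controls the baseline and 8-week surveys and only then an invitation to the program.

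On active questioning, Section 6.10 covers people who leave the study or stop the program early, and says of them: "every effort should be made to gather primary outcome data (pain interference) as well as a query about adverse events". The Section 7.1 schedule has no adverse-event row at any time point.

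**The concern.** A passive method records what staff happen to hear, so its yield depends on how often they speak with participants. Before week 8 that frequency is set by the randomized arm. Two things are at stake.

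The first is complete reporting. A control participant hospitalized in week 3 has no scheduled call until week 8, and no stated question at that call would bring the event out. The reporting duties in Section 7.4.4 cover both arms, so this matters whether or not the arms are ever compared.

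The second is interpretation. Section 1.4.1 accepts that "it is possible that participants could experience an injury while doing physical activity, like muscle strain", and also names psychological distress as a risk. Background illness is expected as well. If events are later set out by arm, a surplus under the intervention could come from more frequent contact alone. Capture is also incomplete in the intervention arm, so real program-related injuries can be missed there too.

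**Working it through.** The plan gives no adverse-event rate or detection figure, so there is nothing to reproduce. The check sets the routes side by side and then asks which way the difference pushes.

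**Routes by arm, up to and including week 8**

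| Route | Intervention | Control | Source |
|---|---|---|---|
| CHW sessions | six | none | 6.2, 7.1 |
| Weekly CHW reminder | yes | none described | 6.2, 6.3 |
| 8-week telephone survey | yes | yes | 5.4, 6.3 |
| Support contact by staff | unscheduled | unscheduled | 7.4.4 |
| Query at withdrawal or on declining to finish the intervention | yes | at withdrawal | 6.10 |
| Adverse-event item in the schedule | none | none | 7.1 |

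Sections 2 and 11.2.2 count 7 sessions and Section 6.2 describes six. That should be reconciled, but it does not alter the comparison.

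**Direction.** Suppose each contact after an event reveals it with probability q. Controls have one scheduled contact, the survey, so detection is q. An intervention participant with m CHW sessions still to come after the event has detection 1 − (1 − q)^(m+1). This is at least q, and equals q only if m = 0 or q = 1 (or q = 0). The extra sessions can only add recorded events.

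**Illustration (q, the timing and the event risk are all assumptions).** Take the same true risk in both arms, event times uniform over 8 weeks, all contacts completed, and CHW sessions at weeks 1 to 6. An event in week 1 is followed by 7 contacts, one in week 2 by 6, and so on down to one in week 6 by 2. Events in weeks 7 and 8 are followed by the survey alone. Average detection in the intervention arm is

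{[sum over k = 2 to 7 of (1 − (1 − q)^k)] + 2q} / 8.

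For q = 0.3 the powers of 0.7 from the 2nd to the 7th sum to 1.441, so detection is (6 − 1.441 + 0.6)/8 = 0.645, against 0.30 in controls: a ratio of 2.15. With 20 per arm (40 randomized 1:1) and an assumed 20% risk, there are 20 × 0.20 = 4 true events per arm. Recorded events are 4 × 0.645 = 2.6 against 4 × 0.30 = 1.2. The chance of recording none is (1 − 0.129)^20 = 6% against (1 − 0.06)^20 = 29%.

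| Assumed q | Ratio, sessions in weeks 1–6 | Ratio, sessions in weeks 2–7 |
|---|---|---|
| 0.1 | 3.0 | 3.5 |
| 0.2 | 2.5 | 2.9 |
| 0.3 | 2.2 | 2.4 |
| 0.5 | 1.6 | 1.75 |
| 0.8 | 1.2 | 1.2 |
| 1.0 | 1.0 | 1.0 |

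The ratio follows entirely from q and the timing. The table shows the direction and how far the answer depends on the assumption; it does not estimate the effect in this trial.

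**After the change.** If both arms are asked the same question at the same call, detection through that item is equal and the ratio is 1.0 for any q, provided that survey completion and readiness to report are similar in the two arms.

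**The case against.** Passive monitoring is a reasoned choice here. Section 7.4.4 justifies it by the low likelihood of events and an 8-week participation period, and calls the study minimal risk. Both arms share a survey call of about 45 minutes, which the section names as a route, and staff are trained to report. Section 6.8 also records participation ended for acute illness or changed disease severity as an adverse event, so capture is not wholly a matter of chance. Some weekly reminders may be texts or voicemails, and Section 6.5 allows for weeks without a session, so contact in the intervention arm is not always a conversation.

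These points limit the weight of the concern. They do not close the gap, because the section that cites low likelihood also expects hospitalizations and requires them to be reported.

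A reader might infer more than the documents support:

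- *That a planned safety comparison is invalid.* Section 11 plans no adverse-event comparison or table by arm, and Section 2 has no safety endpoint.
- *That the statement that benefits outweigh risks is undermined.* Section 1.4.3 is a prospective judgment about a non-invasive program and does not rest on event counts from this trial.
- *That people who leave are asked and those who complete are not.* The survey instrument and the manual of procedures are not in the documents, so one can say only that the protocol states no such question for completers. Section 6.10 also bars further contact with anyone who withdraws completely, so not every leaver will be asked.
- *That controls have no contact at all.* They have no scheduled contact; support or scheduling calls may still reach them.

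**Conclusion.** The point holds as a gap in the capture of reportable events, and as a caution for any later tabulation by arm. It rests on three things in the text: a passive method, CHW contact before week 8 in one arm only, and no adverse-event item in the schedule although serious events are expected and reportable in both arms. Its size cannot be derived from the documents, and any ratio quoted for it restates assumed detection rates. It affects no planned test, and the trial is an unpowered, minimal-risk pilot. The change is worth making because it is cheap and improves both completeness and comparability; nothing here calls the primary analysis into question.

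**What to change.** Add one structured question to the 8-week telephone survey in both arms, asking about any hospitalization, emergency visit, injury, fall or marked distress since baseline. List it in the Section 7.1 schedule and refer to it in Section 7.4.4. If the survey already contains such an item, stating it in those two places is enough. Base any adverse-event summary by arm on this item, and list passively learned events separately by source (CHW, support staff, other).

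The cost is an item or two in a call already planned, a slightly longer interview, an IRB wording amendment and a few more reports to process. A week-8 question does not make reporting of earlier events timely and does not reach people lost to follow-up, so passive reporting should continue alongside it.

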6.9.2 Community Health Worker Training and Tracking

The study CHW will complete the MiCHWA CHW Certification Training Program, a 126-hour course covering topics such as: communication skills and motivational interviewing, documentation and reporting, navigating community resources, and healthy lifestyles.

STEP-UP-specific training will take place over a series of initial training sessions (the equivalent of approximately 4 full days) with ongoing training/feedback by the PI or other members of the study team or research staff throughout the study period. Our CHW training approach has been refined over a series of studies, and emphasizes role play and practice sessions with feedback. We focus on older adults' needs, including multimorbidity and cognitive issues, as well as record-keeping, teaching goal-setting, managing common issues such as temporary increases in pain after activity, and knowing when to consult with a supervisor and the study team.

All intervention sessions with participants will be audio recorded, with participants' permission, and a checklist will be used to determine fidelity to the session protocol in the community health worker STEP-UP manual. We will test for CHW "drift" from the protocol by listening to all sessions for the first 3 participants, and a random 20% of recorded calls thereafter, and offer feedback and additional training as needed. Recording of session information in REDCap (e.g., information from phone sessions such as goals, also reminder calls/texts and whether response was received from participant) will also be audited, on the same schedule. The CHW will meet regularly (weekly or biweekly) with a research staff member for coaching and feedback. The duration of calls will also be recorded.

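### The protocol expects no related adverse events, yet it describes activity injury, distress and post-activity pain increases elsewhere, so one event can be coded expected or not expected and mild ones may be under-recorded

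*Combined protocol and SAP*

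**What the plan says.** The section numbered 7.4.4 (placed within Section 8) states: "No related AEs or SAEs are expected for this minimal-risk study of a behavioral intervention". It explains such events as "events known to be associated with the intervention or condition under study". It then acknowledges that participants will be encouraged to be more active, and sets out a separate class of expected but unrelated events.

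Four other places bear on the same question:

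- Section 1.4.1, Known Potential Risks, lists psychological distress, rated infrequent and mild. It also lists "minor physical injury from doing physical activity that is encouraged by the STEP-UP program", with muscle strain as the example and the same ratings. It does not mention a temporary rise in pain.
- Section 6.9.2 says that CHW training covers "managing common issues such as temporary increases in pain after activity".
- Section 8.3 defines an AE broadly enough to include any unfavorable symptom, related or not. It adds: "The most likely example for the present pilot study is elevated psychological distress".
- Section 8.4.3 says that for an event to be classed as expected "it should have been addressed in at least one of the following sources: this document", and then names further sources.

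On capture, Section 7.4.4 describes passive monitoring. It also requires staff, including CHWs, to be trained to report any possible AE at once, and puts all AEs on a REDCap form. Section 8.4.1 has a grade for mild events that need no treatment.

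**The concern.** Expectedness has consequences in this protocol. Under Section 7.4.4, events that are both serious and unexpected go to the IRB, the NIA Program Officer and the Roybal Directors, while expected or unrelated serious events go into a quarterly summary for the Program Officer and the Directors. If the text supports two answers for one event, its handling depends on which section the staff member consulted.

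The second issue is counting. The protocol judges the risks to be minimal, and the pilot is meant to inform a possible larger trial. Activity-related pain is the harm closest to the primary outcome, pain interference. If mild events of this kind are recorded unevenly, a low count of related AEs could reflect either their absence or a failure to record them, and a reader could not tell which.

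**Working it through.** No figure in the documents bears on this point and no rate is given, so the check is a comparison of text.

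**Step 1. Are these events AEs?** Section 8.3 covers any unfavorable symptom associated in time with participation. Section 8.4.1 grades mild events that need no treatment. A pain flare, a muscle strain or an episode of distress fits.

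**Step 2. Are they expected when judged related or possibly related?**

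| Event | Where the protocol addresses it | Section 8.4.3 | Section 7.4.4 statement |
|---|---|---|---|
| Temporary pain increase after activity | 6.9.2 (called common); absent from 1.4.1 | Can be expected | Not expected |
| Minor musculoskeletal injury | 1.4.1 (infrequent, mild) | Can be expected | Not expected |
| Transient distress | 1.4.1 (infrequent, mild); 8.3 (most likely AE) | Can be expected | Not expected |

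The last two columns disagree in all three rows. Section 7.4.4 also adds a further yardstick: for serious events, unexpected means not defined as expected in the data and safety monitoring plan, which is not among the sources named in Section 8.4.3.

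**Step 3. Does the coding change anything?** For mild events it changes the label. For serious ones it changes the route. The Section 7.4.4 trigger list places an emergency room visit under serious AEs. If such a visit followed a post-activity flare and was judged related, it could go to the quarterly summary under Section 8.4.3, or to the IRB, Program Officer and Directors under the Section 7.4.4 statement.

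**Step 4. Is the likeliest AE stated consistently?** Section 8.3 names distress. Section 1.4.1 rates distress infrequent, while Section 6.9.2 calls post-activity pain increases common. These statements do not fit together if a flare is an AE under Section 8.3.

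**Step 5. How would a mild event reach the AE form?**

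- The schedule in Section 7.1 has no AE item.
- The only direct AE query, in Section 6.10, is for participants who withdraw or decline to finish the intervention.
- The trigger list covers hospitalization, institutionalization, emergency visits, death, severe medical problems and threats of harm. It names no minor event.
- Section 11 plans no AE summary.
- CHW sessions before week 8 take place only in the intervention arm (Sections 6.3 and 7.1). With 40 participants allocated 1:1, about 20 have that route and about 20 do not, so passively collected counts would not be comparable between arms.

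**The case against.** The strongest reply is that the reporting duty is already complete. Section 7.4.4 names CHWs among those trained to report any possible AE, all AEs go on a form, and mild events have a grade. Section 6.9.2 also covers record-keeping and when to consult a supervisor. Coaching a flare and filing it are compatible. This stands, and it rules out a conclusion that a reader might draw, namely that CHWs will not file flares. The text does not direct that; it leaves under-recording possible. Flare-specific instructions may also sit in the CHW manual or the manual of procedures, which are not among these documents.

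A second reply is that the Section 7.4.4 sentence is only a forecast that nothing related will occur. That is hard to sustain, because the section glosses the term as events with a known association and sets a class of expected, unrelated events beside it.

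A third reply is that everyone enrolled already has pain on most days or every day (Section 5.1), so relatedness needs case-by-case judgment on the five-level scale in Section 8.4.2. This also stands, and is why possibly related is the right description.

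A fourth is that worsening pain would be seen anyway, through pain interference and intensity at baseline and week 8, global change at week 8, and review of a sample of recorded sessions. These measures show lasting change in both arms, but they would not reliably show short flares and do not replace AE counts.

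A reader might also infer that flares would become Unanticipated Problems. Section 8.3 requires all three criteria to be met. A minor flare would usually fail the one on greater risk than previously known, and it is hard to call unexpected when the protocol describes it.

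**Conclusion.** The contradiction is real and lies in operative safety text. The same activity-related event or episode of distress can be coded expected under Section 8.4.3 or not expected under Section 7.4.4, and the statement of the likeliest AE conflicts with the frequencies given elsewhere. Under-recording of mild activity-related events is a risk, not a certainty.

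No count can be attached. In Section 6.9.2 the word common describes issues that the training prepares for; it is not an event rate for STEP-UP. Any number of expected flares would rest on an assumed rate, and ranking flares as the likeliest harm would be an inference from that one word.

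The conclusion rests on two readings: that Section 8.4.3 allows an event addressed in the protocol to be called expected, and that Section 8.3 covers a short rise in pain. The events are mild and the primary analysis is unaffected. The point is modest but should be corrected, because it governs how program-related harms are classified and counted.

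**What to change.** 1. Reconcile Sections 1.4.1, 6.9.2, 7.4.4, 8.3 and 8.4.3. In Section 7.4.4, replace the blanket statement with a short list of expected, possibly related events: temporary pain increase after activity, minor musculoskeletal injury and transient distress. Add the pain increase to Section 1.4.1, and align the Section 8.3 example with the stated frequencies.
2. State one recording rule that matches the AE definition in Section 8.3 and the grades in Section 8.4.1. Say explicitly that CHW coaching of a flare does not replace an entry on the existing AE form with grade and relatedness. A threshold limited to flares that stop an activity or lead to care would be narrower than the protocol's own definition, so it should not be introduced silently.
3. Add a by-arm summary of these events to Section 11. Ideally, add one identical AE question to the existing 8-week telephone survey in both arms, so that the comparison does not depend on CHW contact.

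The cost is a few lines of protocol text, one survey item and a line in the CHW manual. The downside is a slightly longer AE list and a less favourable statement on expectedness.
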